## 6.2.2. Hematologic Improvement Response Criteria:

# Proposed Modified International Working Group Response Criteria for Hematologic Improvement Hematologic improvement\*

Erythroid response (pretreatment, < 11 g/dL)

Platelet response (pretreatment, < 100 × 109/L)

Neutrophil response (pretreatment, < 1.0 × 109/L)

Progression or relapse after HI‡

# Response criteria (Responses must last at least 8 weeks)†

Hgb increase by ≥1.5 g/dL Relevant reduction of units of RBC transfusions by an absolute number of at least 4 RBC transfusions/8 wk compared with the pretreatment transfusion number in the previous 8 wk. Only RBC transfusions given for a Hgb of ≤9.0 g/dL pretreatment will count in the RBC transfusion response evaluation†

Absolute increase of ≥30 × 109/L for patients starting with >20 × 109/L platelets Increase from <20 × 109/L to >20 × 109/L and by at least 100%† At least 100% increase and an absolute

increase >0.5 × 109/L† At least 1 of the following:

At least 50% decrement from maximum response levels in granulocytes or platelets

Reduction in Hgb by > 1.5 g/dL Transfusion dependence

Source: (Cheson, et al. 2006) Abbreviations: Hgb indicates hemoglobin; RBC: red blood cell; HI: hematologic improvement. Note: Deletions to the IWG response criteria are not shown. Note: To convert hemoglobin from g/L to g/dL, divide g/L by 10. \*Pretreatment counts averages of at least 2 measurements (not influenced by transfusions) ≥1 week apart (modification).

†Modification to IWG response criteria (Cheson, et al. 2003) ‡In the absence of another explanation, such as acute infection, repeated courses of chemotherapy (modification), gastrointestinal bleeding, hemolysis, and so forth.

For each subject, response to therapy, duration of response, event-free survival, and overall survival will be calculated. The duration of response is defined as the number of

\*Responses must last at least 8 weeks

NCT ID: NCT03047993 Protocol 2016-063 Date: 06/03/2019

Page **25** of **39** 

days from the date of initial response (PR or better) to the date of first documented disease progression/relapse or death, whichever occurs first. Event-free survival is defined as the number of days from the date of treatment initiation (i.e., C1D1) to the date of documented treatment failure, relapses from CR, or death from any cause, whichever occurs first, and will be calculated for all patients. In the event that neither disease progression or death is documented prior to study termination, analysis cutoff, or the start of confounding anticancer therapy, these endpoints will be censored at the

In addition, relationships between anti-tumor activity, PDn markers, exploratory biomarkers, and drug exposure levels will be explored.

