# 1.2 Secondary Objectives

The secondary objectives of the study are:

- 1.2.1. To explore the pharmacokinetics (PK) of telaglenastat in combination with AZA
- 1.2.2. To explore the pharmacodynamics (PDn) of telaglenastat in combination with AZA
- 1.2.3. To assess overall survival, event-free survival and duration of response of telaglenastat in combination with AZA

NCT ID: NCT03047993

Protocol 2016-0636 Date: 06/03/2019

Page **4** of **39** 

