#### 6. RESPONSE DEFINITIONS

### **6.1 Study Endpoints:**

**6.2.1. Efficacy Analysis:** Clinical activity of telaglenastat + AZA will be assessed based on Modified IWG Response Criteria for MDS (Cheson et al, 2006).

Proposed Modified International Working Group Response Criteria for Altering Natural History of MDS Category	Response criteria (Responses must last at least 4 weeks)
Complete remission	Bone marrow: ≤5% myeloblasts with normal maturation of all cell lines* Persistent dysplasia will be noted*† Peripheral blood‡ Hgb ≥11 g/dL Platelets ≥100 × 109/L Neutrophils ≥1.0 × 109/L† Blasts = 0%
Partial remission	All CR criteria if abnormal before treatment except: Bone marrow blasts decreased by ≥50% over pretreatment but still >5% Cellularity and morphology not relevant
Marrow CR†	Bone marrow: ≤5% myeloblasts and decrease by ≥50% over pretreatment† Peripheral blood: if HI responses, they will be noted in addition to marrow CR†
Stable disease	Failure to achieve at least PR, but no evidence of progression for >8 wks

Protocol 2016-0636 Date: 06/03/2019

Page **23** of **39** 

Failure Death during treatment or disease

progression characterized by worsening of cytopenias, increase in percentage of bone marrow blasts, or progression to a more advanced MDS FAB subtype than

pretreatment

Relapse after CR or PR At least 1 of the following: Return to

pretreatment bone marrow blast percentage Decrement of ≥50% from maximum remission/response levels in granulocytes or platelets Reduction in Hgb concentration by ≥1.5 g/dL or

transfusion dependence

Cytogenetic response Complete: Disappearance of the

chromosomal abnormality without

appearance of new ones Partial: At least

50% reduction of the chromosomal

abnormality

Disease progression For patients with: Less than 5% blasts:

≥50% increase in blasts to >5% blasts 5%-10% blasts: ≥50% increase to >10% blasts 10%-20% blasts: ≥50% increase to >20% blasts 20%-30% blasts: ≥50%

increase to >30% blasts

Any of the following: At least 50%

decrement from maximum

remission/response in granulocytes or platelets Reduction in Hgb by ≥2 g/dL

Transfusion dependence

Survival Endpoints: Overall: death from any cause

Event free: failure or death from any cause PFS: disease progression or death from MDS DFS: time to relapse Cause-specific death: death related to MDS

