#### 8.1.2. Phase II:

The Simon minimax two-stage design will be employed for the Phase II portion.(15) We assume a target response rate of 60% and a response rate of 40% or lower will be considered not desirable. Response is defined as complete remission (CR), partial remission (PR), marrow CR (mCR), or Hematologic Improvement (HI) by modified IWG criteria for MDS patients. For example a 29% CR/PR rate was reported in the azacitidine arm in the randomized AZA-001 trial, and a 23% CR/PR rate and 60% ORR (including 37% HI) was seen in the azacitidine arm of the CALGB 9221 trial. To implement the Simon's two-stage design, the assessment window for response (CR+PR+mCR+HI) is defined as response occurring within the first 6 cycles of treatment. With a type I error rate of 10% and 80% power, we will enroll 16 patients in the first stage. If 6 or fewer patients achieve response, enrollment will be halted. If 7 or more out of the first 16 patients achieve response, accrual will continue until a total of 28 patients have been enrolled. If 15 or more out of these 28 patients achieve response, the treatment will be considered efficacious and worthy of further investigation. Under this Simon's minimax two-stage design, the probability of early termination is 53% and the expected sample size is 22 if the true response rate is 40%.

Protocol 2016-0636 Date: 06/03/2019

Page **34** of **39** 

A Toxicity Summary will be submitted to the IND Office Medical Monitor after the first 7 evaluable patients and every 7 evaluable patients thereafter.

A Response Summary will be submitted to the IND Office Medical Monitor after 15 evaluable patients complete 6 cycles of study treatment.

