#### 8.3. Analysis Plan:

During Phase II portion, if 6 or fewer patients out of the first 16 patients achieve response, enrollment will be halted. If 7 or more out of the first 16 patients achieve response, accrual will continue until a total of 28 patients have been enrolled. If 15 or more out of these 28 patients achieve response, the treatment will be considered efficacious and worthy of further investigation. The rates of response (CR+PR+mCR+HI) to therapy will be estimated along with the 95% confidence interval. The Kaplan-Meier method will be used to estimate the probabilities of event-free survival (EFS), overall survival (OS) and duration of response. Log-rank tests will be used to compare among subgroups of patients in terms of EFS, OS or duration of response. Anti-tumor activity, PDn markers, exploratory biomarkers and drug exposure levels will be summarized graphically and with descriptive statistics. Safety data will be summarized using frequency and percentage, by category and severity.

Protocol 2016-0636 ate: 06/03/2019

Page **36** of **39** 

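### Duration of response starts only at PR or better, so HI-only responders, and probably marrow CR responders, who count toward the go/no-go rule have no duration.

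*Combined protocol and SAP*

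**What the plan says.** Section 8.1.2 sets the endpoint for the Simon design: "Response is defined as complete remission (CR), partial remission (PR), marrow CR (mCR), or Hematologic Improvement (HI"), counted if it occurs within the first 6 cycles. Section 8.3 uses the same set: "The rates of response (CR+PR+mCR+HI) to therapy will be estimated along with the 95% confidence interval".

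Section 6.2.2, in the text after the HI criteria, defines duration of response as the number of "days from the date of initial response (PR or better) to the date of first documented disease progression/relapse or death". The sentence just before it says that duration of response is calculated for each subject.

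Duration of response is a secondary objective in Section 1.2.3: "To assess overall survival, event-free survival and duration of response of telaglenastat in combination with AZA". Section 8.3 uses Kaplan-Meier to "estimate the probabilities of event-free survival (EFS), overall survival (OS) and duration of response", adds log-rank comparisons between subgroups, and gives no other definition of duration.

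The response table in Section 6.2.1 lists marrow CR as a category of its own, after PR, and defines stable disease by not having reached PR. Section 6.2.2 gives HI its own criteria, including a rule for progression or relapse after HI.

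**The concern.** The plan uses the word response for two different groups. One decides whether the treatment is worth further study; the other is the group whose durability is reported. The second is a subset of the first, and nothing says that the narrowing is intended. The presence of a relapse rule for HI suggests an oversight: HI responders have a defined end event but no start date.

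At stake is Section 1.2.3. The trial could meet its 15-of-28 rule largely on HI and marrow CR, then report a duration of response for a minority of those responders under the same name. There is also a timing effect. A patient who reaches HI first and PR later does get a duration, but it is counted from the later date.

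**Working it through.** **1. The plan's own design figures.** Inputs from Section 8.1.2: first stage 16 patients, stop at 6 or fewer responses; total 28, success at 15 or more; response rates 40% and 60%.

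- Early termination at 40%: P(X ≤ 6), X ~ Bin(16, 0.40) = 0.527 (plan: 53%).
- Expected sample size: 16 + (1 − 0.527) × 12 = 21.7 (plan: 22).
- Probability of success: sum over x = 7 to 16 of P(X = x) × P(Y ≥ 15 − x), with Y ~ Bin(12, p). This gives 0.099 at p = 0.40 (plan: type I error 10%) and 0.803 at p = 0.60 (plan: power 80%).

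A search over all designs up to 28 patients returns this one as the minimax design. The figures reproduce, and none of them depends on how duration of response is defined.

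**2. Who has a start date.**

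| Category | Response in 8.1.2 and 8.3 | Duration starts under 6.2.2 | Loss rule in the tables |
|---|---|---|---|
| CR | yes | yes | relapse after CR or PR; disease progression |
| PR | yes | yes | relapse after CR or PR; disease progression |
| Marrow CR | yes | not stated; probably no | disease progression only |
| HI only | yes | no | progression or relapse after HI |

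**3. How many responders this could be.** Section 8.1.2 says of one azacitidine trial that "a 23% CR/PR rate and 60% ORR (including 37% HI) was seen in the azacitidine arm". For a second trial it gives a 29% CR/PR rate and no overall response rate.

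- Share without a duration, first trial: 37/60 = 61.7%; share with one: 23/60 = 38.3%.
- Share without a duration, 29% CR/PR against an assumed 60% response rate: 1 − 29/60 = 51.7%.
- Expected responders at the 60% target: 0.60 × 28 = 16.8.
- With a duration: 0.23 × 28 = 6.4, or 0.29 × 28 = 8.1.
- Without: 16.8 − 6.4 = 10.4, or 16.8 − 8.1 = 8.7.

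At exactly 15 responders, the same shares leave 15 × 37/60 = 9.3, or 15 × 31/60 = 7.8, without a duration.

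**4. Sensitivity.** If the overall response rate were 40% and the CR/PR rates stayed at 23% to 29% (an assumption), the share without a duration would be 1 − 23/40 = 42.5% to 1 − 29/40 = 27.5%. The gap shrinks but remains.

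**The case against.** The best defence is that duration of CR/PR is a legitimate endpoint, that duration of response here is secondary and descriptive, and that some minimum durability is already built in: HI must last at least 8 weeks and the Section 6.2.1 responses at least 4 weeks. All of that is true. It supports keeping the CR/PR curve under a clear label. It does not explain why the responders who can carry the decision have no duration.

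Four stronger readings are tempting, and the documents do not support them.

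- **Marrow CR is certainly excluded.** The table order and the stable-disease definition point that way. However, marrow CR requires blasts at or below 5%, while PR leaves them above 5%, so on marrow alone it is the deeper response. PR or better is never mapped to the categories.
- **The CR/PR subset has a better prognosis.** The documents give no figure or statement on this.
- **The 62% figure is the expected loss.** It is the upper end of a range. The quoted rates are for azacitidine without telaglenastat and show no marrow CR category.
- **Relapse after PR escapes event-free survival.** The definition does name only "relapses from CR, or death from any cause", while the table row is "Relapse after CR or PR". But documented treatment failure is also an event, and the Failure row covers progression shown by worsening cytopenias or rising marrow blasts. Most, if not all, PR relapses would fall there. This is a wording mismatch, not a separate error.

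**Conclusion.** The mismatch is real and unresolved in the documents. It is certain for HI-only responders and probable for marrow CR. On the plan's quoted CR/PR rates and a 60% response rate, about 52% to 62% of responders, roughly 9 to 10 of about 17, would have no duration of response. The Kaplan-Meier estimate, and any log-rank subgroup comparison of it, would rest on about 6 to 8 patients. These counts assume that the response mix resembles the azacitidine reference trials and, for the 29% rate, that it sits within a 60% overall rate. The true mix is unknown.

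The go/no-go rule, type I error, power and sample size are untouched. The consequence is confined to Section 1.2.3, which would go unanswered for many of the patients behind the primary result. The change should be made, but it does not threaten the design.

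**What to change.** In Section 6.2.2, define duration of response for every patient counted as a responder under Section 8.1.2. It should run from the first qualifying CR, PR, marrow CR or HI to the matching loss of response or death, whichever comes first:

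- **CR or PR:** relapse after CR or PR, or disease progression, per the Section 6.2.1 table.
- **Marrow CR:** disease progression per the same table, including its blast-based criteria, since there is no relapse row for marrow CR.
- **HI:** progression or relapse after HI, per Section 6.2.2.

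Keep the present definition as a separate curve labelled duration of CR/PR, and state whether marrow CR belongs in it. Refer to both curves in Section 8.3. While editing, align the relapse wording in event-free survival with the table, so that it covers relapse from CR or PR.

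The cost is one extra Kaplan-Meier curve. Section 5.2.4 already schedules hematology on day 1 of every cycle and marrow at set cycles; the sponsor should confirm that transfusion dates are captured, because transfusion dependence is one of the loss criteria. The drawback is that the all-responder curve pools response types with different loss criteria, so show it by response category as well.

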### 4.2. Study Duration:

- 4.2.1. All subjects must complete a screening visit, day 1 visits for each new cycle, and an end-of-treatment visit.
- 4.2.2. Treatment will continue until discontinuation due to relapse, unacceptable toxicity, or disease progression as defined by the IWG 2006 criteria for MDS. This includes:
  - clinically significant progressive disease at any time, or

NCT ID: NCT03047993

Protocol 2016-0636 ate: 06/03/2019

Page **15** of **39** 

- a lack of clinical benefit after 5 cycles of treatment at the highest dose of study medication, or
- Possibility of undergoing allogeneic stem cell transplantation
- discontinuation of study drug for more than 6 weeks, or
- intercurrent illness that prevents further administration of treatment, or
- unacceptable adverse event(s), or
- patient decision for study withdrawal, or
- general or specific changes in the patient's condition that render the patient unacceptable for further treatment in the judgment of the investigator

Patients may remain on study for up to 12 cycles if the patient demonstrates clinical benefit and no excessive toxicity (i.e. no clinically significant study-drug related grade  $\geq$  3 toxicity). Patients who are experiencing clinical benefit and have not experienced excessive toxicity may be eligible to continue therapy after discussion with the PI and the discussion documented in the patient's medical record.

If one of the study agents is discontinued due to toxicity, the patient may remain on study until the occurrence of significant disease progression, severe toxicity that requires all study agents to be permanently discontinued, or at the discretion of the PI.

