## 6.2.3. Primary Safety Endpoint

date of last tumor assessment date.

Primary safety endpoint: The overall incidence and severity of all adverse events using Common Toxicity Criteria v 4.0.

An adverse event is any untoward medical occurrence that may present during treatment with a pharmaceutical product but which does not necessarily have a causal relationship with this treatment. Adverse events (AEs) will be collected using the Leukemia AE guidelines.

Adverse drug reaction is a response to a drug which is noxious and unintended and which occurs at doses normally used in man for prophylaxis, diagnosis, or therapy of disease or for the modification of physiologic function.

All "suspected adverse reactions" (as defined in 21 CFR 312.32(a)) will be captured in the case report forms. For abnormal chemical values grade 3 or 4, the apogee will be reported per course in the CRF.

Assessing causal connections between agents and disease is fundamental to the understanding of adverse drug reactions. In general, a drug may be considered a contributory cause of an adverse event if, had the drug not been administered, 1) the event would not have happened at all, 2) the event would have occurred later than it actually did, or 3) the event would have been less severe.

The Investigator or physician designee is responsible for verifying and providing source documentation for all adverse events and assigning the attribution for each event for all subjects enrolled on the trial.

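### EFS censors stable-disease patients who stop for lack of benefit and start new therapy, and drops their later deaths; a supplementary analysis that does not censor there would show the effect cheaply.

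*Combined protocol and SAP*

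**What the plan says.** EFS is a secondary objective (Section 1.2.3). Section 6.2.2, after the hematologic improvement criteria, runs EFS from C1D1 to "documented treatment failure, relapses from CR, or death from any cause, whichever occurs first, and will be calculated for all patients". The survival entry of the response table in Section 6.2.1 is shorter: "Event free: failure or death from any cause".

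The same table has two grounds for failure. One is a death while on treatment. The other is given as "progression characterized by worsening of cytopenias, increase in percentage of bone marrow blasts, or progression to a more advanced MDS FAB subtype than" at baseline. Stable disease, meaning less than a PR without progression, is a separate category.

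The censoring sentence in Section 6.2.2 covers patients in whom neither progression nor death has been recorded by one of three points: the end of the study, the data cutoff, and a third that it words as "or the start of confounding anticancer therapy, these endpoints will be censored at the". The date it then names, printed under the next heading, is the "date of last tumor assessment date".

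Among the reasons to stop treatment, Section 4.2.2 lists "a lack of clinical benefit after 5 cycles of treatment at the highest dose of study medication" as an item of its own, apart from progressive disease. After discontinuation, Section 5.4 describes follow-up for survival only. Section 8.3 estimates EFS by Kaplan-Meier and names no sensitivity analysis for it.

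**The concern.** Kaplan-Meier treats a censored patient as having the same future as patients still at risk at that time. Here the plan's own stopping rule picks out patients who have not benefited. If such a patient is stable and moves to another therapy, the censoring sentence takes the patient out at the last assessment. The reason for leaving is related to prognosis, so the assumption is doubtful for exactly this group.

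There is also a conflict within Section 6.2.2. EFS counts death from any cause and is to be calculated for all patients. Yet a death after new therapy starts, which Section 5.4 does collect, falls after the censoring date and is lost to EFS.

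The trial has one arm, so any upward shift in the EFS curve is not offset by a similar shift in a control arm. EFS does not drive a decision in this trial, so the stake is how accurately a named secondary endpoint is described.

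**Working it through.** The documents state no EFS rate, median or stopping rate, so there is no plan figure to reproduce. The check is a reading of the text followed by an assumed example.

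**What happens to each type of patient under the text as written**

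| Patient | EFS status |
|---|---|
| Documented failure or progression, or relapse from CR, before new therapy | Event |
| Death before new therapy | Event |
| Stable disease, stops for lack of benefit, no new therapy | Not censored by the new-therapy clause; a later death still counts |
| Stable disease, stops for lack of benefit, starts new therapy | Censored at the last tumor assessment; a later death is not counted |

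Only the last row is at issue. Separately, the censoring sentence names progression and death, while the event list names failure, relapse from CR and death. The two lists do not match.

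**Size of the bias in an assumed example**

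Assumptions, none of them from the documents except the timing:
- EFS is exponential with a 12-month median for everyone up to the stop, and afterwards for those who continue.
- The stop comes after 5 cycles: 5 × 28 = 140 days, about 4.6 months. This coincides with the C6D1 marrow in Section 5.2.4.
- A share *p* of those event-free at month 4.6 stops. All of them start new therapy and are censored at that time.
- Stoppers have a remaining median time to progression or death of *m* months.

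Formulas:
- Event-free at 4.6 months: 0.5^(4.6/12) = 0.767
- Continuers, from month 4.6 to 12: 0.5^(7.4/12) = 0.652
- Stoppers, from month 4.6 to 12: 0.5^(7.4/m), which is 0.425 for m = 6 and 0.277 for m = 4
- Reported 12-month EFS with stoppers censored: 0.767 × 0.652 = 50%, whatever *p* is
- True 12-month EFS: 0.767 × [(1 − p) × 0.652 + p × 0.5^(7.4/m)]

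| p (of those event-free at 4.6 months) | Share of all patients (0.767 × p) | Reported | True, m = 6 | True, m = 4 | True, m = 12 |
|---|---|---|---|---|---|
| 10% | 8% | 50% | 48.3% | 47.1% | 50% |
| 20% | 15% | 50% | 46.5% | 44.3% | 50% |
| 30% | 23% | 50% | 44.8% | 41.4% | 50% |
| 40% | 31% | 50% | 43.0% | 38.5% | 50% |

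The overstatement is therefore about 2 to 12 percentage points when stoppers do worse, and zero when their prognosis is the same (m = 12).

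**A different quantity, not to be confused with bias**

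Counting every such stop as an event gives 50% × (1 − p) = 45%, 40%, 35% and 30% for the same values of *p*. That gap appears even when stoppers' prognosis is no worse. It measures a change of endpoint definition, not an error in the Kaplan-Meier estimate.

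**The case against.** The strongest reply is that treatment failure is already an EFS event. A reader might infer that the plan removes from the risk set the patients in whom treatment failed. The documents do not support that: documented failure, relapse from CR and death before new therapy all count. The table's failure entry includes worsening cytopenias without a numeric threshold, so some non-benefiting patients will be events on that ground. Section 4.2.2 also lists the 5-cycle stop under a lead-in about relapse, toxicity and progression, so an investigator might record it as treatment failure. If that is intended, those patients are events and the problem goes away for them. But Section 6.2.2 does not say so, and the only definition of failure given points the other way. EFS would then depend on an unwritten coding choice.

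A reader might also take the 60% response target to mean that up to 40% of patients are censored this way. That does not follow. Non-responders include early progressions and deaths, which are events, as well as toxicity stops. The documents give no rate for lack-of-benefit stops or for new therapy.

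It is also fair to say that the documents cite no historical EFS for azacitidine, only response rates and response duration, so a misleading historical comparison cannot be shown from them. OS is analysed separately and keeps the later deaths. Counting stops as events is a different estimand rather than a correction, which is why it belongs beside the current analysis and not in its place.

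**Conclusion.** The point holds in a limited form and is a cheap improvement. Followed literally, the plan censors stable-disease patients who stop for lack of benefit and start new therapy, for a reason related to prognosis, and omits their later deaths from an endpoint defined by death from any cause. If they fare worse than patients who continue, EFS is biased upward.

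The size cannot be derived from the documents. With a 12-month median EFS, 10% to 40% of those event-free at month 4.6 censored at the stop, and a remaining median of 4 to 6 months in stoppers, true 12-month EFS is about 48% down to about 38.5%, against 50% reported. Patients who go to transplant, if transplant counts as confounding therapy, need not follow the same direction. The two-stage rule (7 of 16, then 15 of 28) uses response only and is unaffected.

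**What to change.** In Section 6.2.2:
- Align the censoring sentence with the EFS event list: failure, relapse from CR, death.
- State whether a stop for lack of benefit is documented treatment failure.

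In Section 8.3:
- Keep the current EFS analysis and add one prespecified supplementary Kaplan-Meier analysis that does not censor at new therapy. In it, discontinuation for lack of benefit or start of new anticancer therapy, other than transplant in ongoing response, is an event on that date. For patients not given such an event, deaths after new therapy count.
- Report the number of patients censored at new therapy in the current analysis.

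The cost is one extra analysis and an EFS figure that will look less favourable. The new-therapy date is already needed to apply the current rule, and deaths are already collected under Section 5.4. Treatment rules do not change.
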